## 3.1.2 Secondary Effectiveness Endpoints

The secondary effectiveness endpoints identified for this Early Feasibility Study for IOPCL AMD-MAG are:

- Proportion of eyes (≥ 50%) able to achieve 20 letters or more of uncorrected near visual acuity (at 14 cm) at 12 months from baseline.
- Proportion of eyes (≥75%) able to achieve improvement of 10 letters or more when comparing uncorrected near visual acuity (UCNVA) (at 14 cm) at 12 months from baseline BCNVA (at 30 cm, wearing the appropriate preoperative distance refractive correction in addition to +3.0D add).

- Proportion of eyes (≥50%) able to achieve improvement of 20 letters or more when comparing uncorrected near visual acuity (UCNVA) (at 14 cm) at 12 months from baseline BCNVA (at 30 cm, wearing the appropriate preoperative refractive distance correction addition to +3.0D add).
- Proportion of eyes (≥ 75%) able to achieve improvement of 10 letters or more when comparing best corrected near visual acuity (BCNVA) (at 14 cm) at 12 months from baseline BCNVA (at 30 cm, wearing the appropriate preoperative distance refractive correction in addition to +3.0D add).
- Proportion of eyes (≥ 50%) able to achieve improvement of 20 letters or more when comparing best corrected near visual acuity (BCNVA) (at 14 cm) at 12 months from baseline BCNVA (at 30 cm, wearing the appropriate preoperative distance refractive correction in addition to +3.0D add).

# 3.1.3 Exploratory Effectiveness Endpoints

The following exploratory effectiveness endpoints evaluated for eyes that achieve  $\geq 20$  letters of improvement in UCNVA during preoperative simulation testing.

- Proportion of eyes (≥ 75%) achieving improved reading speed (at 40 cm) at 12 months from baseline defined as ≥ 2 lines/blocks of gain with a decrease in reading speed ≥ 1 minute and with overall improvement in critical point size
- Proportion of eyes (≥ 75%) achieving independence from external magnifier usage at 12 months postoperatively

# 3.2 Safety Endpoints

• Preservation of Best Corrected Distance Visual Acuity (BCDVA)

The preservation of BCDVA is defined as proportion of eyes (< 5%) that lose two or more lines (≥10 letters) of BCDVA at 12 months from baseline.

• Preservation of Best Corrected Near Visual Acuity (BCNVA)

Proportion of eyes (<5%) that lose two or more lines of BCNVA (≥10 letters on the Sloan Near Vision Chart at 14 cm) at 12 months from baseline.

- Incidence of secondary surgical intervention (SSI)
- Successful Delivery of the IOPCL as determined as all postoperative scheduled visits starting at 7-14 days postoperative.

The successful delivery of the IOPCL is defined as no capsular tear, no visible damage to either the IOL or IOPCL, and uniform leaflet coverage of all IOPCL haptic tabs.

• Long-term Adherence and Positional Stability

The long-term adherence and positional stability is defined as 1) minimal change in uniformity of the gap between consecutive scheduled visits at 1-2 months and later as determined by UBM imaging (where minimal change is defined as +/- 10 microns between visits established and maintained using UBM imaging).

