4.1. Safety Endpoints

- Preservation of BCDVA Proportion of eyes (< 5%) that lose two or more lines of BCDVA (≥10 letters on the ETDRS chart) at 12 months from baseline.
- Preservation of BCNVA Proportion of eyes (<5%) that lose two or more lines of BCNVA
 (≥10 letters on the Sloan Near Vision Chart at 14 cm) at 12 months from baseline.
- Incidence of secondary surgical intervention (SSI).
- Successful delivery of the IOPCL AMD-MAG as determined at all postoperative scheduled visits starting at 7-14 days post-operative.
 - No capsular tear
 - No visible damage to either the PCIOL or the IOPCL AMD MAG
 - o Uniform leaflet coverage of all IOPCL AMD MAG haptic tabs
- Long-term adherence and positional stability
 - O Gap: Minimal change in uniformity of the gap between consecutive scheduled visits at 1-2 months and later as determined by UBM measurements. Minimal change is defined as +/- 10 microns between visits is established and maintained using UBM imaging.
 - o Tilt:
- Tilt of the PCIOL as determined at all post-operative scheduled visits starting at 30-60 days post-operative. Minimal tilt of the PCIOL confirmed via penlight examination and defined as ≤ 10 degrees between the postoperative tilt of the PCIOL and the pre-operative tilt of the PCIOL.
- Tilt of the IOPCL AMD-MAG as determined at all post-operative scheduled visits starting at 30-60 days post-operative. Minimal tilt of the IOPCL AMD-MAG (using the PCIOL as a reference point) confirmed via penlight examination and defined as ≤ 10 degrees between the post-operative tilt of the. PCIOL and the postoperative tilt of the IOPCL AMD-MAG.
- O Decentration: Decentration as determined at all post-operative scheduled visits starting at 7-14 days post-operative. Centration of the IOPCL AMD-MAG (using the PCIOL as a reference point) confirmed during slit lamp examination and defined as uniform exposed area of the PCIOL outside of the IOPCL AMD-MAG at the vertical and horizontal meridians between ≥ 0.25 mm and ≤ 0.75 mm.
- Counts and percentages for incidence of cumulative and persistent intraoperative and post-operative adverse events
- Counts and percentages for incidence of secondary surgical interventions (e.g., removal
 of interlenticular opacity, repositioning of IOPCL, explant of IOPCL, repositioning of
 PCIOL) (excluding Nd:YAG treatments for PCO).

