5.1. Inclusion Criteria

- 1. Subjects aged 55 years or older.
- 2. Subjects who have already had cataract surgery with an Alcon SN60WF, SA60AT or SA60WF monofocal intraocular lens with a lens power between 17.0 diopters and 24.0 diopters clearly evidenced by photographic documentation by one of the following:
 - patient medical record
 - clinic chart with labeling attached
 - surgical record with labeling attached, or
 - patient identification card with make, model and serial number.
- 3. Subjects who have already had cataract surgery at least 6 months from the planned date of the IOPCL surgery.
- 4. Subjects with non-neovascular dry AMD or stable wet AMD meeting the following criteria:
 - No macular fluid retention in the past 12 months
 - No treatment within the past 12 months
 - No change in Amsler Grid test within the past 12 months
 - No subretinal fluid or macular hemorrhage confirmed by optical coherence tomography (OCT) imaging.
 - No fundoscopic changes within the past 12 months (i.e., changes in retinal pigment epithelium).
- 5. Subjects with best corrected distance visual acuity from 20/80 to 20/800.
- 6. Subjects with a preoperative manifest refraction spherical equivalent (MRSE) of +1.0D to -1.0D.
- 7. Subjects with ≤1.0D of corneal cylinder determined by keratometry readings.
- 8. Subjects who are unsatisfied with their current near vision correction provided by either spectacles or external magnifier.
- 9. Subjects who have experienced and failed one or more high-magnification refractive correction alternatives to the IOPCL AMD-MAG.

- 10. Subjects who demonstrate at least 10 letters of near visual acuity improvement with the simulation/tolerance test (using manifest refraction with +7.0D add) compared to conventional near vision testing (using manifest refraction with +3.0D add).
- 11. Subjects with a minimum endothelial cell count of 1800 cells/mm².
- 12. Subjects willing to abstain from pursuing any other surgical vision-correcting procedures for the duration of the study.
- 13. Subjects who are willing and able to complete all required postoperative visits.
- 14. Subjects who are able to comprehend and sign a statement of informed consent.

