6.1. Outcome Simulation Testing

After informed consent has been obtained the subject will be required to participate in a "Outcome Simulation test." First, the subject's manifest refraction will be placed in a trial frame. Next, using the add power of commonly-used spectacles, a +3.0D lens will be placed into the trial frame and near visual acuity will be tested using the Sloan Near Vision Chart at 30 centimeters (11.5 inches) and at the subject's preferred reading distance (i.e., the distance at which the subject can most clearly see the chart or reading material). Then, the +3.0D lens will be exchanged for a +7.0D lens and near visual acuity will be assessed using the Sloan chart at 14 centimeters (5.5 inches) and the

subject's preferred reading distance. This will closely simulate the expected outcome after surgery and determine if he/she can tolerate the high magnification. Subjects who demonstrate at least 10 letters of near visual acuity improvement with the +7.0D lens, compared to near visual acuity achieved with the +3.0D lens, will have the option to continue with the remaining pre-operative testing or to withdraw from the study. Subjects who fail to achieve at least 10 letters of near visual acuity improvement with the simulation testing or who are not completely tolerant of their vision during the simulation testing will be exited from the study.

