15. CLINICAL ASSESSMENTS

All parameters will be recorded for both eyes at baseline (pre-operative). Measurements will be recorded for the study eye at postoperative and post-removal visits. See Appendix 2A schedule of visits (pre- and post-operative visits) and Appendix 2B (post-removal visits). See Appendix 3 for clinical assessment instructions.

Order of Clinical Assessments:

- Mesopic contrast sensitivity testing should be performed prior to the slit lamp examination
 and before any visual acuity testing that requires bright light directed at the subject (i.e., a
 reading lamp shined directly over the subject's shoulder onto the reading card).
- Confirmation of IOPCL location should be performed after the study eye is dilated.

Study sites are expected to implement COVID-19 pandemic safety measures in accordance with their local, state, and CDC health guidelines to ensure the health and well-being of the subjects and study staff who come in contact with the subjects.

Clinical Assessments and Timepoints

- Inclusion/exclusion criteria: Preoperative
- Medical history: Preoperative
- External magnifier usage: Preoperative, 30-60 days, 120-180 days, 330-420 days. Interim
 - Post-removal, 30-60 days, 120-180 days, 330-420 days, Interim
- Demographics: Preoperative
- Patient Informed Consent: Preoperative
- Capsulorhexis Size at the time of PCIOL surgery: Preoperative
- Position of PCIOL Haptics and Planned IOPCL Incision Location: Preoperative
- Axial Length: Preoperative
- Keratometry: Preoperative

- Mesopic and Photopic Pupil size measured by Pupillometer: Preoperative.
- Pseudophakic PCIOL power with make and model number: Preoperative.
- Simulation of expected outcome (3.0D lens over manifest refraction at 30cm and 7.0D lens over manifest refraction, at 14cm and preferred distance): Preoperative.
- Ocular Dominance: Preoperative
- Optical Coherence Tomography: Preoperative, 30-60 days, 120-180 days, 330-420 days.
 Interim
 - Post-removal, 30-60 days, 120-180 days, 330-420 days, Interim
- Capsular Stability: Preoperative, Operative, 7-14 days, 30-60 days, 120-180 days, 330-420 days, Interim
 - Post-removal, 7-14 days, 30-60 days, 120-180 days, 330-420 days, Interim
- Spatial Visualization between the PCIOL and IOPCL Using UBM: 30-60 days, 120-180 days, 330-420 days, Interim.
- Recording of the IOPCL Surgical Procedure: Operative
- IOPCL Location and Confirmation of Incision Location: Operative

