- IOPCL Location (following dilation): 1-2 days, 7-14 days, 30-60 days, 120-180 days, 330-420 days, Interim
- Manifest Refraction: Preoperative, 7-14 days, 30-60 days, 120-180 days, 330-420 days, Interim
 - Post-removal, 7-14 days, 30-60 days, 120-180 days, 330-420 days, Interim
- Add Power: Pre-Operative, 7-14 days, 30-60 days, 120-180 days, 330-420 days, Interim.
 - Post-removal, 7-14 days, 30-60 days, 120-180 days, 330-420 days, Interim
- BCDVA: Best Corrected Distance Visual Acuity (at 6m) Preoperative, 7-14 days, 30-60 days, 120-18 days, 330-420 days, Interim
 - Post-removal, 7-14 days, 30-60 days, 120-180 days, 330-420 days, Interim
- BCNVA: Best Corrected Near Visual Acuity (at 30 cm (preoperatively); 14 cm (postoperatively) and preferred reading distance (preoperatively and postoperatively)) Pre-Operative, 7-14 days, 30-60 days, 120-180 days, 330-420 days, Interim.
 - Post-removal, 7-14 days, 30-60 days, 120-180 days, 330-420 days, Interim

- UCDVA: Uncorrected Distance Visual Acuity (at 6m)— Preoperative, 7-14 days, 30-60 days, 120-180 days, 330-420 days.
 - Post-removal, 7-14 days, 30-60 days, 120-180 days, 330-420 days. Interim
- UCNVA: Uncorrected Near Visual Acuity (at 14 cm and preferred reading distance) –
 Preoperative, 7-14 days, 30-60 days, 120-180 days, 330-420 days
 - Post-removal, 7-14 days, 30-60 days, 120-180 days, 330-420 days, Interim
- Central Visual Field (Amsler Grid): Preoperative
- Reading Speed (Smith-Kettlewell testing at 40 cm): Preoperative, 7-14 days, 30-60 days, 120-180 days, 330-420 days
 - Post-removal, 7-14 days, 30-60 days, 120-180 days, 330-420 days, Interim
- Contrast Sensitivity (Mesopic): Preoperative, 7-14 days, 30-60 days, 120-180 days, 330-420 days
 - Post-removal, 7-14 days, 30-60 days, 120-180 days, 330-420 days, Interim
- Slit Lamp Examination: Preoperative, 1-2 days, 7-14 days, 30-60 days, 120-180 days, 330-420 days, Interim.
 - Post-removal, 1-2 days, 7-14 days, 30-60 days, 120-180 days, 330-420 days, Interim
- Gonioscopy: 7-14 days, 30-60 days, 120-180 days, 330-420 days, Interim
 - Post-removal, 7-14 days, 30-60 days, 120-180 days, 330-420 days, Interim
- Intraocular Pressure: Preoperative, 1-2 days, 7-14 days, 30-60 days, 120-180 days, 330-420 days, Interim
 - Post-removal, 1-2 days, 7-14 days, 30-60 days, 120-180 days, 330-420 days, Interim
- Dilated Fundoscopy: Preoperative, 7-14 days, 30-60 days, 120-180 days, 330-420 days, Interim

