#### 7.5.2 Preservation of BCNVA

The analysis of this clinical outcome will be based on the observed data of IOPCL AMD-MAG. The number and percent of IOPCL implanted eyes with a BCNVA loss of 2 or more lines (≥10 letters) at 12 months from preoperative will be derived.

Additionally, if needed, data listing or summary will be provided for eyes with a BCNVA loss of  $\geq 2$  lines from the best BCNVA before the corresponding visits.

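### The BCNVA safety endpoint names neither the distance nor the add of its baseline; the likely default sets 14 cm against 30 cm and can leave a loss of two or more lines at 14 cm uncounted

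*SAP*

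**What the plan says.** SAP 3.2 counts eyes that "lose two or more lines of BCNVA (≥10 letters on the Sloan Near Vision Chart at 14 cm) at 12 months from baseline", with a goal below 5%. Protocol 4.1 has the same definition ("≥10 letters on the Sloan Near Vision Chart at 14 cm) at 12 months from baseline"). Neither gives a distance or add for the baseline. The analysis in SAP 7.5.2 gives no distance for either visit: "The number and percent of IOPCL implanted eyes with a BCNVA loss of 2 or more lines (≥10 letters) at 12 months from preoperative". It adds, only where needed, a listing or summary of eyes down two or more "lines from the best BCNVA before the corresponding visits".

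The schedule in Protocol 15 changes the distance between visits: "Best Corrected Near Visual Acuity (at 30 cm (preoperatively); 14 cm (postoperatively) and preferred reading distance", the last at both times. A corrected 14 cm score does exist before surgery, but under another name. In the simulation test of Protocol 6.1, "the +3.0D lens will be exchanged for a +7.0D lens and near visual acuity will be assessed using the Sloan chart at 14 centimeters". Protocol 15 lists it as "Simulation of expected outcome (3.0D lens over manifest refraction at 30cm and 7.0D lens over manifest refraction, at 14cm and preferred distance): Preoperative".

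Inclusion criterion 10 admits "Subjects who demonstrate at least 10 letters of near visual acuity improvement with the simulation/tolerance test (using manifest refraction with +7.0D add", compared with a +3.0D add. It gives adds but no distances.

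**The concern.** The endpoint is meant to show that near vision is preserved. A loss can be read from two scores only if they are taken under comparable conditions, or if the difference in conditions is stated and intended. Here the preoperative score that carries the BCNVA label was taken at 30 cm, and the 12-month score is taken at 14 cm. Eyes are enrolled because they read better with the stronger add. On the scheduled reading, that gain is credited to the eye before any loss is counted, so an eye that became clearly worse at 14 cm could be reported as preserved.

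The study is not masked (SAP 6.3). If the baseline is left open, it could be chosen after the scores are known, and with so few eyes that choice could decide whether the goal is met.

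**Working it through.** The documents derive no figure for this endpoint; SAP 6.2 only caps the sample at 10 eyes. The check is therefore direct arithmetic.

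**Inputs**
- Loss threshold: 10 letters, or two lines (Protocol 4.1, SAP 3.2).
- Goal: below 5% of eyes (same sections).
- Preoperative scores: 30 cm with +3.0D and 14 cm with +7.0D (Protocol 6.1). Postoperative BCNVA: 14 cm (Protocol 15).
- Entry gain: at least 10 letters, +7.0D over +3.0D (Protocol 5.1).

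**Step 1: what the default reading counts.** Let g = preoperative 14 cm score − preoperative 30 cm score, and let L = preoperative 14 cm score − 12-month 14 cm score. The scored change is the 12-month 14 cm score − the preoperative 30 cm score = g − L. An eye is counted if g − L ≤ −10, that is, if L ≥ 10 + g.

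| g (letters) | Loss at 14 cm needed to be counted |
|---|---|
| 0 | 10 |
| 5 | 15 |
| 10 | 20 (4 lines) |
| 15 | 25 |
| 20 | 30 |

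If criterion 10 is scored at 30 cm and 14 cm, only rows with g of 10 or more can occur. Protocol 6.1 also tests both adds at preferred distance. If that comparison decides entry, any row can occur.

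**Step 2: an example.** Before surgery an eye reads 30 letters at 30 cm and 40 at 14 cm; at 12 months it reads 25 at 14 cm. Its loss at 14 cm is 40 − 25 = 15 letters (3 lines). The default reading scores 30 − 25 = 5 letters, and the eye is not counted.

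**Step 3: the same with test noise.** With normal error, the chance of counting an eye with true loss L is Φ((L − 10 − g)/SD). For L = 15, the matched 14 cm comparison (no g term) counts it with probability 0.84 at an SD of change of 5 letters and 0.69 at 10. The default reading with g = 10 gives 0.16 and 0.31. The SDs are assumptions.

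**Step 4: the goal.** One event is 1/10 = 10% of 10 eyes and 1/5 = 20% of 5. Even 1/20 = 5.0% is not below 5%; the first size that allows one event is 21 (1/21 = 4.8%). With at most 10 eyes, the goal is met only with zero events.

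**Step 5: the price of a matched baseline.** For an unchanged eye the chance of a false flag is p = Φ(−10/SD), and for at least one of 10 eyes it is 1 − (1 − p)^10. Enrolling on an observed gain favours 14 cm scores that were high by chance, which raises p. The last column simulates this (assumed mean true gain 10 to 20 letters, between-eye SD 5, normal errors, entry at an observed gain of 10 or more).

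| SD of change (assumed) | p, no selection | At least one of 10, no selection | At least one of 10, with selection |
|---|---|---|---|
| 5 | 0.023 | 21% | 22% to 31% |
| 7 | 0.077 | 55% | 59% to 73% |
| 10 | 0.159 | 82% | 87% to 94% |

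**The case against.** The strongest reply is that the baseline is less open than it looks. Wherever the documents spell out baseline BCNVA (Protocol 4.4, SAP 3.1.2 and 7.4.2), it is 30 cm with +3.0D, and the comparison of 14 cm with 30 cm is made openly there. Read that way, the safety endpoint asks whether the implanted eye at its working distance sees worse than it did with an ordinary reading add. That is a legitimate question. This stands, and it is why the 30 cm comparison should be kept. It does not settle the text, because the safety endpoint itself names only 14 cm. The primary endpoint has the same short form and is matched, since uncorrected near acuity is scheduled at 14 cm before and after surgery.

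A reader might infer that the +7.0D simulation score is the only correct baseline. The documents do not support that. Protocol 6.1 presents the test as a simulation of the expected result, so a shortfall may mean that the device missed its simulation rather than that sight was lost. The optics also differ: a trial-frame lens before surgery, an intraocular central zone after it. The false-flag rates above weigh against using this score alone.

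A reader might also infer that a loss of 10 to 19 letters is always hidden. That holds only if entry is scored at the fixed distances.

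Other measures give partial cover. Distance acuity at 6 m, reading speed at 40 cm and mesopic contrast sensitivity are taken before and after surgery, so a severe visual loss need not go unseen, but none of them is near acuity at 14 cm. The table by visit in SAP 7.5.7.2 gives acuity categories without a distance. The listing against the best earlier score is conditional and could miss a loss already present at the first postoperative test.

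Appendices 3 (clinical methods) and 8 (case report forms) were not available and may state distance, add and scoring.

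**Conclusion.** The point holds: this rule can give a wrong safety result, and more than a wording detail is at stake. The endpoint leaves its baseline distance and add unstated, and the schedule leads to a 14 cm score set against a 30 cm, +3.0D score. The resulting offset is g letters, at least 10 under fixed-distance entry and without a guaranteed minimum otherwise. The mismatch of conditions remains in either case.

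One uncounted eye is enough to change whether the goal is met. It would be too strong to say that this alters the conduct of the trial: the summaries are descriptive (SAP 6.1), no hypothesis is tested, and the stopping rules in Protocol 4.2 do not use this endpoint. The conclusion rests on the supplied text, without Appendices 3 and 8. The offset arithmetic needs no assumed SD; the detection and false-flag probabilities do.

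**What to change.** In Protocol 4.1 and SAP 3.2 and 7.5.2:

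- Name the baseline distance and add, and state the correction worn for the 12-month score.
- Always report two counts at 12 months: eyes that lost 10 or more letters from the 30 cm, +3.0D score, and eyes that lost 10 or more letters from the preoperative 14 cm, +7.0D score.
- Fix before 12-month data are seen which count is judged against 5%.
- List every eye flagged on either comparison with both preoperative scores and the 12-month score.

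The cost is wording, one table and one listing. Both preoperative scores are already collected under Protocol 6.1, so no test or visit is added. The downside is that the 14 cm count may flag unchanged eyes, and a flag may reflect a shortfall from the simulation. It should therefore be read beside the 30 cm count, not alone. The listing lets a reader tell a loss just over 10 letters from a large one.

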## • Tilt

- O Tilt of the PCIOL as determined at all post-operative scheduled visits starting at 30-60 days post-operative. Minimal tilt of the PCIOL confirmed via penlight examination and defined as  $\leq$  10 degrees between the postoperative tilt of the PCIOL and the pre-operative tilt of the PCIOL.
- o Tilt of the IOPCL AMD-MAG as determined at all post-operative scheduled visits starting at 30-60 days post-operative. Minimal tilt of the IOPCL AMD-MAG (using the PCIOL as a reference point) confirmed via penlight examination and defined as ≤ 10 degrees between the post-operative tilt of the PCIOL and the postoperative tilt of the IOPCL AMD-MAG.

